### **C. First treatment visit (day 1)**

1. Physical examination, including vital signs, symptoms assessment, and ECOG performance score (not required if already obtained within 14 days)
2. Blood draw CBC, chemistry panel, PSA and PAP. May be done up to 7 days in advance of Day 1, and could coincide with screening evaluation.
3. pTVG-HP immunization intradermally on the deltoid area of the lateral arm (preferentially left arm) with 0.25 mL administered at each of two adjacent sites
4. Following vaccination, subjects will be observed for 60 min. for adverse events

5. Nivolumab 240 mg, administered intravenously over 30 minutes

D. Second treatment visit (week 2, 14 +/- 3 days after day 1 visit)

1. Symptoms assessment
2. pTVG-HP immunization intradermally on the deltoid area of the lateral arm (preferentially left arm) with 0.25 mL administered at each of two adjacent sites
3. Following vaccination, subjects will be observed for 60 min. for adverse events
4. Nivolumab 240 mg, administered intravenously over 30 minutes

E. Third treatment visit (week 4, 14 +/- 3 days after week 2 visit)

1. Physical examination, including vital signs, symptoms assessment, and ECOG performance score
2. Blood draw CBC, chemistry panel, PSA and PAP. NOTE: for this visit the PSA can be obtained up to 7 days prior to the visit in order to have the results available to determine whether rhGM-CSF will be co-administered.
3. 10 ml peripheral blood (red-top tube) for sera to evaluate baseline antibody responses, and 100 ml peripheral blood (green-top heparinized tubes) for T-cell response evaluation
4. pTVG-HP immunization intradermally on the deltoid area of the lateral arm (preferentially left arm) with 0.25 mL administered at each of two adjacent sites
5. NOTE: If serum PSA obtained at this visit is higher than that obtained at day 1 visit, then rhGM-CSF (208 µg) will be co-administered with the pTVG-HP immunization as adjuvant for this and all subsequent immunizations
6. Following vaccination, subjects will be observed for 60 min. for adverse events
7. Nivolumab 240 mg, administered intravenously over 30 minutes

F. Fourth treatment visit (week 6, 14 +/- 3 days after week 4 visit)

1. Symptoms assessment
2. pTVG-HP immunization intradermally on the deltoid area of the lateral arm (preferentially left arm) with 0.25 mL administered at each of two adjacent sites: NOTE: If serum PSA obtained at week 4 was higher than that obtained at day 1 visit, then rhGM-CSF (208 µg) will be co-administered with the pTVG-HP immunization as adjuvant for this and all subsequent immunizations
3. Following vaccination, subjects will be observed for 60 min. for adverse events
4. Nivolumab 240 mg, administered intravenously over 30 minutes

G. Fifth treatment visit (week 8, 14 +/- 3 days after week 6 visit)

1. Physical examination, including vital signs, symptoms assessment, and ECOG performance score
2. Blood draw CBC, chemistry panel, PSA and PAP.
3. pTVG-HP immunization intradermally on the deltoid area of the lateral arm (preferentially left arm) with 0.25 mL administered at each of two adjacent sites NOTE: If serum PSA obtained at week 4 was higher than that obtained at day 1

visit, then rhGM-CSF (208 µg) will be co-administered with the pTVG-HP immunization as adjuvant for this and all subsequent immunizations

4. Following vaccination, subjects will be observed for 60 min. for adverse events
5. Nivolumab 240 mg, administered intravenously over 30 minutes

H. Sixth treatment visit (week 10, 14 +/- 3 days after week 8 visit)

1. Symptoms assessment
2. pTVG-HP (+/- GM-CSF adjuvant) immunization intradermally on the deltoid area of the lateral arm (preferentially left arm) with 0.25 mL administered at each of two adjacent sites NOTE: If serum PSA obtained at week 4 was higher than that obtained at day 1 visit, then rhGM-CSF (208 µg) will be co-administered with the pTVG-HP immunization as adjuvant for this and all subsequent immunizations
3. Following vaccination, subjects will be observed for 60 min. for adverse events
4. Nivolumab 240 mg, administered intravenously over 30 minutes

I. Seventh treatment visit (week 12, 14 +/- 3 days after week 10 visit)

1. Physical examination, including vital signs, symptoms assessment, and ECOG performance score
2. Blood draw CBC, chemistry panel, PSA and PAP.
3. 10 ml peripheral blood (red-top tube) for sera to evaluate baseline antibody responses, and 100 ml peripheral blood (green-top heparinized tubes) for T-cell response evaluation
4. pTVG-HP (+/- GM-CSF adjuvant) immunization intradermally on the deltoid area of the lateral arm (preferentially left arm) with 0.25 mL administered at each of two adjacent sites NOTE: If serum PSA obtained at week 4 was higher than that obtained at day 1 visit, then rhGM-CSF (208 µg) will be co-administered with the pTVG-HP immunization as adjuvant for this and all subsequent immunizations
5. Following vaccination, subjects will be observed for 60 min. for adverse events
6. Nivolumab 240 mg, administered intravenously over 30 minutes
7. NaF PET/CT (NaF PET/CT within +/- 7 days of week 12 study visit, exceptions may be allowed with prior approval from the study PI ). NOTE: This PET scan is for research purposes only and will not be used for clinical response evaluation or treatment decisions. This study will be performed only at designated sites. NaF PET/CT should NOT be obtained within 2 days of GM-CSF injection.

J. Eighth treatment visit (week 16, 28 +/- 3 days after week 12 visit)

Ninth treatment visit (week 20, 28 +/- 3 days after week 16 visit)

1. Physical examination, including vital signs, symptoms assessment, and ECOG performance score
2. Blood draw CBC, chemistry panel, PSA and PAP.
3. pTVG-HP (+/- GM-CSF adjuvant) immunization intradermally on the deltoid area of the lateral arm (preferentially left arm) with 0.25 mL administered at each of two adjacent sites NOTE: If serum PSA obtained at week 4 was higher than that

obtained at day 1 visit, then rhGM-CSF (208 µg) will be co-administered with the pTVG-HP immunization as adjuvant for this and all subsequent immunizations

4. Following vaccination, subjects will be observed for 60 min. for adverse events
5. Nivolumab 240 mg, administered intravenously over 30 minutes

K. Tenth treatment visit (week 24, 28 +/- 3 days after week 20 visit)

1. Physical examination, including vital signs, symptoms assessment, and ECOG performance score
2. Blood draw CBC, chemistry panel, PSA and PAP (can be performed +/- 7 days of this visit)
3. CT scan of abdomen and pelvis, and bone scan (can be performed +/- 7 days of this visit)
4. 10 ml peripheral blood (red-top tube) for sera to evaluate baseline antibody responses, and 100 ml peripheral blood (green-top heparinized tubes) for T-cell response evaluation (can be performed +/- 7 days of this visit)
5. pTVG-HP (+/- GM-CSF adjuvant) immunization intradermally on the deltoid area of the lateral arm (preferentially left arm) with 0.25 mL administered at each of two adjacent sites NOTE: If serum PSA obtained at week 4 was higher than that obtained at day 1 visit, then rhGM-CSF (208 µg) will be co-administered with the pTVG-HP immunization as adjuvant for this and all subsequent immunizations
6. Following vaccination, subjects will be observed for 60 min. for adverse events
7. Nivolumab 240 mg, administered intravenously over 30 minutes
8. NaF PET/CT (NaF PET/CT within +/- 7 days of week 24 study visit, exceptions may be allowed with prior approval from the study PI.). NOTE: This PET scan is for research purposes only and will not be used for clinical response evaluation or treatment decisions. This study will be performed only at designated sites. NaF PET/CT should NOT be obtained within 2 days of GM-CSF injection.

L. Eleventh treatment visit (week 28, 28 +/- 3 days after week 24 visit)

Twelfth treatment visit (week 32, 28 +/- 3 days after week 28 visit)

1. Physical examination, including vital signs, symptoms assessment, and ECOG performance score
2. Blood draw CBC, chemistry panel, PSA and PAP.
3. pTVG-HP (+/- GM-CSF adjuvant) immunization intradermally on the deltoid area of the lateral arm (preferentially left arm) with 0.25 mL administered at each of two adjacent sites NOTE: If serum PSA obtained at week 4 was higher than that obtained at day 1 visit, then rhGM-CSF (208 µg) will be co-administered with the pTVG-HP immunization as adjuvant for this and all subsequent immunizations
4. Following vaccination, subjects will be observed for 60 min. for adverse events
5. Nivolumab 240 mg, administered intravenously over 30 minute

M. Thirteenth treatment visit (week 36, 28 +/- 3 days after week 32 visit)

1. Physical examination, including vital signs, symptoms assessment, and ECOG performance score
2. Blood draw CBC, chemistry panel, PSA and PAP.
3. 10 ml peripheral blood (red-top tube) for sera to evaluate baseline antibody responses, and 100 ml peripheral blood (green-top heparinized tubes) for T-cell response evaluation
4. pTVG-HP (+/- GM-CSF adjuvant) immunization intradermally on the deltoid area of the lateral arm (preferentially left arm) with 0.25 mL administered at each of two adjacent sites NOTE: If serum PSA obtained at week 4 was higher than that obtained at day 1 visit, then rhGM-CSF (208 µg) will be co-administered with the pTVG-HP immunization as adjuvant for this and all subsequent immunizations
5. Following vaccination, subjects will be observed for 60 min. for adverse events
6. Nivolumab 240 mg, administered intravenously over 30 minutes

N. Fourteenth treatment visit (week 40, 28 +/- 3 days after week 36 visit)

Fifteenth treatment visit (week 44, 28 +/- 3 days after week 40 visit)

1. Physical examination, including vital signs, symptoms assessment, and ECOG performance score
2. Blood draw CBC, chemistry panel, PSA and PAP.
3. pTVG-HP (+/- GM-CSF adjuvant) immunization intradermally on the deltoid area of the lateral arm (preferentially left arm) with 0.25 mL administered at each of two adjacent sites NOTE: If serum PSA obtained at week 4 was higher than that obtained at day 1 visit, then rhGM-CSF (208 µg) will be co-administered with the pTVG-HP immunization as adjuvant for this and all subsequent immunizations
4. Following vaccination, subjects will be observed for 60 min. for adverse events
5. Nivolumab 240 mg, administered intravenously over 30 minute

O. End of treatment period visit (week 48, 28 +/- 3 days after week 44 visit)

1. Physical examination, including vital signs, symptoms assessment, and ECOG performance score
2. Blood draw CBC, chemistry panel, PSA and PAP (can be performed +/- 7 days of this visit).
3. CT scan of abdomen and pelvis, and bone scan (can be performed +/- 7 days of this visit)
4. 10 ml peripheral blood (red-top tube) for sera to evaluate baseline antibody responses, and 100 ml peripheral blood (green-top heparinized tubes) for T-cell response evaluation (can be performed +/- 7 days of this visit)

P. Week 60 visit (84 +/- 14 days after week 48 visit)

1. Physical examination, including vital signs, symptoms assessment, and ECOG performance score
2. Blood draw CBC, chemistry panel, PSA and PAP.

Q. Week 72 visit (84 +/- 14 days after week 60 visit)

1. Physical examination, including vital signs, symptoms assessment, and ECOG performance score
2. Blood draw CBC, chemistry panel, PSA and PAP.
3. CT scan of abdomen and pelvis, and bone scan (can be performed +/- 7 days of this visit)

R. Week 84 visit (84 +/- 14 days after week 72 visit)

1. Physical examination, including vital signs, symptoms assessment, and ECOG performance score
2. Blood draw CBC, chemistry panel, PSA and PAP.

S. Week 96 visit (84 +/- 14 days after week 72 visit) – END OF STUDY

1. Physical examination, including vital signs, symptoms assessment, and ECOG performance score
2. Blood draw CBC, chemistry panel, PSA and PAP.
3. CT scan of abdomen and pelvis, and bone scan (can be performed +/- 7 days of this visit)

T. 28-Day Follow Up Visit (28 +/- 7 days after Off-study date, if prior to week 48)

Patients will come off study at the time of disease progression, undue toxicity, or at the discretion of the patient and/or treating physician that it is not in the interest of the patient to continue treatment. A separate follow-up visit is not required for patients completing the week 48 evaluation, however for patients coming off study prior to week 48, 28-day follow up visit will include the following:

1. Physical examination, symptoms assessment, and ECOG performance score.
2. Blood draw for CBC, chemistry panel, serum PSA and PAP
3. IF NOT ALREADY COLLECTED WITHIN PREVIOUS 60 DAYS: 10 ml peripheral blood (red-top tubes) for sera to evaluate antibody responses, and 100 ml peripheral blood (green-top heparinized tubes) for T-cell response evaluation

U. Long-term Follow-Up

Subjects will be contacted by telephone (if not already being seen in clinic) annually for 2 years following the last DNA vaccination to collect clinical information to identify any potential long-term risks. This information has been requested by FDA for all gene delivery trials to assess potential long-term risks. The specific information to be collected annually will include:

- Date of contact
- Current medications
- Hospitalizations (dates and reasons for hospital admission)

- Stage of prostate cancer, treatments for prostate cancer, and recent serum PSA level
- New cancer diagnoses
- New autoimmune disorders
- New hematologic or neurologic disorders
- Other new medical diagnoses
- Date of death if patient deceased

## 9. Response Monitoring

### A. Radiographic Monitoring – Primary Endpoint

CT scans of the abdomen and pelvis and bone scans will be obtained at 6-month intervals, or at times clinically indicated at the discretion of the treating physician. Progression is defined as the appearance of metastases by radiographic imaging using the same criteria as for defining study eligibility – RECIST 1.1 criteria (appearance of a visceral lesion > 10 mm by CT or MRI, lymph node > 15 mm in short axis, or appearance of new lesions on bone scan consistent with metastatic disease).

PSA rise will not be used to define disease progression, however PSA progression will be determined, as per Section 13 below.

### B. Immunological Monitoring

Blood (up to 220 mL) will be collected pre-immunization, and at weeks 4,12, 24, 36, and 48 after study start for immunological monitoring. From the heparinized blood peripheral blood mononuclear cells (PBMC) will be prepared by density centrifugation over Ficoll-Paque using standard techniques (included in separate laboratory manual). PBMC will be cryopreserved in liquid nitrogen using 90% autologous serum collected at the time of blood draw, or 90% fetal calf serum, and 10% DMSO. Sera will be prepared from the red-top tubes and stored in aliquots at –80°C for antibody analyses.

#### (1) Quantitative assessment of PAP-specific CD8+ T-cell effector immunity

PAP-specific IFN $\gamma$ - and granzyme B-secreting T-cell precursor frequency quantification by ELISPOT: ELISPOT will be used as the preferred methodology, as it permits analysis of low-frequency events (LOD < 1:10,000 cells) and also permits simultaneous analysis of cryopreserved batched specimens. Specifically, cryopreserved PBMC from subjects at the various time points will be rapidly thawed, and then transferred to 96-well nitrocellulose microtiter (ELISPOT) plates previously coated with monoclonal capture antibodies specific for IFN $\gamma$  or granzyme B. 10^5 cells per well will be cultured in the presence of media (RPMI 1640 supplemented with L-glutamine, penicillin/streptomycin,  $\beta$ -mercaptoethanol and 10% human AB serum) only (no antigen), 2  $\mu$ g/ml PAP protein, 2  $\mu$ g/ml PSA protein (negative control), 250 ng/ml tetanus toxoid, or 2.5  $\mu$ g/ml PHA (positive mitogenic control) for 24-48 hours. Plates will then be washed with PBS containing 0.05% Tween-20 and incubated for 2.5 hours at room temperature with 50  $\mu$ l/well PBS containing 5  $\mu$ g/ml biotinylated detection antibodies for either IFN $\gamma$  or granzyme B. After incubation, wells

will be washed with PBS, and further incubated with 100  $\mu$ l/well streptavidin-labeled alkaline phosphatase (BioRad, Hercules, CA) and then developed with 100  $\mu$ l/well BCIP/NBT colorimetric substrate (BioRad). The colorimetric reaction will be stopped by rinsing the plates under cool tap water, and wells will be allowed to dry completely before spots are enumerated with an ELISPOT automatic plate reader. Fluorometric assays of detection may be substituted for those described above, and include the evaluation of other cytokines.

**REPORTING AND RESPONSE DEFINITION:** Results will be presented as previously reported as the mean (+/- standard deviation) number of spot-forming-units (sfu) per  $10^6$  cells (frequency), calculated by subtracting the mean number of spots obtained from the no antigen control wells from the mean number obtained in the experimental wells, normalized to  $10^6$  starting PBMC, from 3- to 8-well replicate assays [17]. Comparison of experimental wells with control, no antigen, wells will be performed using a two-sample t-test, with  $p < 0.05$  (two-sided) defined as a significant antigen-specific T-cell response. A significant antigen-specific response resulting from immunization will then be defined as a PAP-specific response detectable at least twice post treatment that is significantly higher than to media only (as above), at least 3-fold higher than the mean baseline value, and with a frequency  $> 10$  per  $10^6$  PBMC.

## (2) Quantitative assessment of antigen-specific antibody immunity

Enzyme-linked immunosorbent assay (ELISA) for the detection of antibodies responses to PAP: The presence of a coexisting humoral immune response to PAP will be evaluated by ELISA using an indirect method similar to that described previously [24]. Specifically, Immulon-4 ELISA plates (Dynex Technologies Inc.) will be coated with 2  $\mu$ g/ml purified PAP protein (Research Diagnostics, Inc.) in 0.1 M NaHCO3/Na2CO3 buffer (pH 9.6) overnight at 4°C. After blocking with PBS/1% BSA for 1 hour at room temperature, wells will be washed with PBS + 0.05% Tween-20 (PBS-Tween) and then incubated for 1 hour with human sera diluted 1:25, 1:50, 1:100 and 1:200. After washing, plates will then be sequentially incubated with a peroxidase-conjugated anti-human IgG detection antibody (Amersham), followed by peroxidase enzyme TMB substrate (Kierkegaard and Perry Laboratories). The color reaction will be stopped with 1N H2SO4 and the optical density measured at 450 nm. Antibody titers for PAP-specific IgG antibodies will be determined as previously described [24].

**REPORTING AND RESPONSE DEFINITION:** These are not strictly quantitative assays. IgG response will be reported graphically demonstrating sera dilution curves, and by titer – defined as the highest sera dilution at which IgG responses are detectable above the mean + 3 standard deviations of the negative control. A positive IgG response resulting from immunization will be defined as an antigen-specific IgG titer at least 4-fold higher than the baseline titer detectable at the 6-month post-treatment time point (or other post-treatment time point evaluated).

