## **2. Background and Rationale**

### **A. PAP is a tumor antigen in prostate cancer and CTL are necessary to destroy prostate tissue**

PAP was first identified in 1938 and was initially used as a serum marker for the detection of prostate cancer [8, 22]. PAP expression in normal and malignant prostate cells is well-documented, and is still used in immunohistochemical staining to establish a prostate origin of metastatic carcinoma [23]. The ubiquitous expression of PAP in prostate tissue makes it an appealing antigen as a potential “universal” target for immune-directed therapies of prostate cancer, unlike specific oncogenes that may or may not be expressed by a particular tumor. Moreover, it has been demonstrated that some patients with prostate cancer have preexisting antibody and T-cell responses to PAP, suggesting that tolerance to this “self” protein can be circumvented *in vivo* [24, 25]. In particular, the demonstration of Th1-like immune responses specific for PAP suggest that an immune environment permissive of an anti-tumor response can exist in patients even without immunization.

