#### Laboratory/Exploratory Biomarker Objectives:

1. To determine if antigen-specific T-cell and/or IgG responses are elicited with treatment

2. To determine if the development of PAP-specific T-cell immune responses are associated with PSA response (decline  $\geq 50\%$ )
3. To determine if antigen spread (the development of immune responses to other cancer-associated proteins) is associated with PSA response (decline  $\geq 50\%$ )
4. To determine if Quantitative Total Bone Imaging (QTBI) by NaF PET/CT can identify bone lesions in this patient population not detected by standard bone scintigraphy
5. To determine whether the presence of lesions detected by NaF PET/CT at baseline is associated with early disease progression (within 1 year) by standard radiographic imaging methods (CT and bone scintigraphy)
6. To determine if growth rates, and changes in growth rates, determined by NaF PET/CT are associated with PSA doubling time and changes in PSA doubling time

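### On the ELISA dilutions as written, a patient whose baseline PAP titer is 1:100 or 1:200 cannot be scored as an IgG responder

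*Combined protocol and SAP*

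**What the plan says.** Protocol Section 9.B(2) describes an indirect ELISA for IgG against PAP. The plates are incubated with "human sera diluted 1:25, 1:50, 1:100 and 1:200". The titer is "defined as the highest sera dilution at which IgG responses are detectable above the mean + 3 standard deviations of the negative control". A positive response resulting from immunization is "an antigen-specific IgG titer at least 4-fold higher than the baseline titer", judged at six months or at another post-treatment time.

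The section refers titer determination to an earlier published method (reference 24). It cautions that the assay is not strictly quantitative, and it also plans to plot the dilution curves. It states no dilution beyond 1:200, no titration to endpoint, and no rule for a baseline near the top or below the bottom of the series.

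Section 2.A says that "some patients with prostate cancer have preexisting antibody and T-cell responses to PAP". The eligibility criteria in Section 5 do not exclude such patients. The IgG result serves laboratory/exploratory objective 1 in Section 3: "To determine if antigen-specific T-cell and/or IgG responses are elicited with treatment".

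**The concern.** A fourfold rule works only if the assay can read at least four times the baseline. Here the response definition and the dilution series sit in the same section, and they do not fit each other at the upper end of the series. A patient who starts high is put among the non-responders whatever the treatment does, and nothing in the data would show that this had happened.

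Section 2.A makes pre-existing antibody foreseeable in this disease. If some of these patients start at 1:100 or above, the reported IgG response rate is too low for a reason that has nothing to do with immunogenicity.

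There is a related gap at the lower end. A baseline that is not detectable at 1:25 has no titer to multiply by four, and the section assigns none. The choice could then be made after the data are seen.

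**Working it through.** The plan states no sample size, power or expected rate for the IgG response, so there is no planned figure to reproduce. The check is a complete enumeration.

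**Inputs, from Section 9.B(2).** Possible detectable titers (reciprocals): 25, 50, 100, 200. Response rule: post-treatment titer ÷ baseline titer ≥ 4.

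**Step 1: largest observable rise.** Formula: 200 ÷ baseline. Titer needed to respond: 4 × baseline.

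| Baseline | Titer needed | Largest observable rise | Can be a responder? |
|---|---|---|---|
| 1:25 | 4 × 25 = 100 | 200 ÷ 25 = 8-fold | Yes, at 1:100 or 1:200 |
| 1:50 | 4 × 50 = 200 | 200 ÷ 50 = 4-fold | Yes, only at 1:200 |
| 1:100 | 4 × 100 = 400 | 200 ÷ 100 = 2-fold | No; 1:400 is not tested |
| 1:200 | 4 × 200 = 800 | 200 ÷ 200 = 1-fold | No; 1:800 is not tested |

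**Step 2: how many patients.** The documents give neither a frequency nor a titer distribution for pre-existing PAP antibody. As an assumption, let 0% to 20% of patients have a baseline of 1:100 or more. Section 10.C plans 41 patients in all, or 21 if the trial stops after stage 1.

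- 41 patients: 0 × 41 = 0, up to 0.20 × 41 = 8.2, so 0 to 8.
- 21 patients: 0 × 21 = 0, up to 0.20 × 21 = 4.2, so 0 to 4.

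At the upper end, the highest response rate that could be observed is (41 − 8) ÷ 41 = 80% or (21 − 4) ÷ 21 = 81%. At the lower end there is no bias.

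**Step 3: baseline undetectable at 1:25.** If it is assigned 12.5, the rule needs 4 × 12.5 = 50, so 1:50, 1:100 and 1:200 all count. If it is assigned 25, the rule needs 4 × 25 = 100, so only 1:100 and 1:200 count. A patient who moves from undetectable to 1:50 is a responder under one convention and not under the other.

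**Step 4: would a longer fixed series be enough?** Suppose all sera, baseline included, are run to 1:800. Every baseline that the present series can return is then covered, since the highest of them, 1:200, needs 800. But 1:400 and 1:800 become possible baselines, and these need 4 × 400 = 1600 and 4 × 800 = 3200, which that series does not reach. The ceiling moves but does not go away.

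**The case against.** The strongest reply is that the titers are to be determined by a cited earlier method. That source was not available for this review. If it provides for further dilution of sera that are positive at 1:200, or for extrapolation, the ceiling does not exist in practice. This stands as a caveat. Against it, the section lists its own dilutions and gives its own titer definition, and neither mentions going further.

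A second reply is that the assay is acknowledged not to be strictly quantitative and that dilution curves will be shown, so a rise in a high-baseline patient might still be visible. That is fair for the graphs. It does not repair the yes/no definition, which is tied to the titer.

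A third reply is that a detailed SAP is promised before analysis (Section 10.D(1)). The rule for undetectable baselines could be set there. An unmeasured dilution could not, unless the laboratory runs it.

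Two stronger readings are tempting and are not supported:

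- A reader might infer that every patient with pre-existing antibody is counted as a non-responder. The enumeration shows otherwise: baselines of 1:25 and 1:50 can meet the rule.
- A reader might infer that a known share of the trial is misclassified. Section 2.A speaks only of some patients and gives no titers, so the number with a baseline of 1:100 or more may be zero.

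**Conclusion.** The point holds on the text as written. With dilutions ending at 1:200, the fourfold rule cannot be met from a baseline of 1:100 or 1:200, so any bias this ceiling causes in the binary IgG response rate is downward. Its size is unknown: 0 to 8 of 41 patients, or 0 to 4 of 21, if 0% to 20% have such baselines. That range is an assumption, and the conclusion also assumes that the cited method adds no further dilutions.

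The reach is narrow. Only the binary PAP IgG response under exploratory objective 1 is affected. It would be wrong to infer that the efficacy conclusion or the other immune analyses are compromised. The PSA complete response endpoint, the stopping rules and the sample size do not use this measure. The T-cell and antigen-spread responses, which exploratory objectives 2 and 3 relate to PSA response, have their own definitions in Sections 9.B(1) and 9.B(3). This is a minor correction, worth making because it is cheap.

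**What to change.** In Section 9.B(2), make three changes:

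1. State that any serum still positive at 1:200 is titrated to endpoint. Alternatively, first establish each patient's endpoint baseline titer and run that patient's post-treatment sera at least two twofold steps beyond it (for example, to 1:400 for a baseline of 1:100 and to 1:800 for a baseline of 1:200). Apply the fourfold rule to the endpoint titers. If the cited method already does this, one sentence saying so is enough.
2. Fix in advance the value for a baseline undetectable at 1:25, and state its consequence. Assigning 1:12.5 makes 1:50 a response; assigning 1:25 requires 1:100. The first is the more lenient choice. Either is workable if chosen before the data are seen.
3. Report how many patients have a baseline of 1:100 or more, so that readers can see whether the issue arose.

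The cost is some extra wells. Section 9.B already has sera stored in aliquots, so no new blood draws are needed.
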